4.3. Justification for Dose

The proposed single SC dose levels are 80 mg and 160 mg. These doses are selected based on the safety and tolerability in Studies CS1 and CS2, and the dosages for the Phase 2b study that is planned in patients with dyslipidemia (Study C4491011). In Study C4491011, the safety and efficacy of a dose range of 80 mg Q4W to 160 mg Q2W will be evaluated. Based on the simulation results using a preliminary population PK-PD model developed from the combined data in Studies CS1 and CS2, vupanorsen 80 mg Q4W is expected to be a minimal efficacious dose in non-HDL-C reduction, and to bridge the data from previous studies. Vupanorsen 160 mg Q2W is expected to achieve a $>90\%$ probability of a $\geq 35\%$ mean reduction in non-HDL-C, in addition to maximizing ANGPTL3 and TG reductions. Thus, 80 mg and 160 mg are selected as the proposed dose level in the current study to cover the potential range of Phase 3 doses (lowest to highest) per dose.

As described in [Section 2.2.2.3](#), vupanorsen single SC doses of up to 120 mg and multiple SC doses of up to 60 mg QW \times 6 doses were generally safe and well-tolerated in healthy participants in Study CS1. Assuming dose-proportional exposure based on the observed mean PK values following a single 80 mg dose of vupanorsen (higher dose-normalized exposure than 120 mg), plasma AUC_{48h} and C_{max} after single SC administration at 160 mg dose are predicted to be 7.94 $\mu\text{g}\cdot\text{h}/\text{mL}$ and 0.676 $\mu\text{g}/\text{mL}$, respectively. The predicted safety margins on AUC_{48h} and C_{max} are 12-fold and 20-fold, respectively, relative to the AUC_{48h} of 95.6 $\mu\text{g}\cdot\text{h}/\text{mL}$ and C_{max} of 13.6 $\mu\text{g}/\text{mL}$ at NOAEL (12 mg/kg/week) in monkeys. The PK, PD and safety data at these dose levels in the upcoming Japan Phase 1 study C4491006 will further support the dose selection in this study.

4.4. End of Study Definition

A participant is considered to have completed the study if he/she has completed all phases of the study, including the last scheduled procedure shown in the [SoA](#).

The end of the study is defined as the date of last scheduled procedure shown in the [SoA](#) for the last participant in the trial.

5. STUDY POPULATION

This study can fulfill its objectives only if appropriate participants are enrolled. The following eligibility criteria are designed to select participants for whom participation in the study is considered appropriate. All relevant medical and nonmedical conditions should be taken into consideration when deciding whether a particular participant is suitable for this protocol.

Prospective approval of protocol deviations to recruitment and enrollment criteria, also known as protocol waivers or exemptions, is not permitted.

5.1. Inclusion Criteria

Participants are eligible to be included in the study only if all of the following criteria apply:

Age and Sex:

1. Male and female Chinese participants must be 18 to 65 years of age, inclusive, at the time of signing the ICD.
 - Refer to [Appendix 4](#) for reproductive criteria for male ([Section 10.4.1](#)) and female ([Section 10.4.2](#)) participants.
 - Chinese participant is defined as individuals currently residing in mainland China who were born in China and have both parents of Chinese descent.

Type of Participant and Disease Characteristics:

2. Male and female Chinese participants who are overtly healthy as determined by medical evaluation including medical history, physical examination, laboratory tests (except for TG levels), and 12-lead ECG monitoring.
3. Fasting TG ≥ 90 mg/dL at Screening (up to 1 repeat allowed for TG and the second TG value will be used for the eligibility).
4. Participants who are willing and able to comply with all scheduled visits, treatment plan, laboratory tests, lifestyle considerations, and other study procedures.

Weight:

5. BMI of 17.5 to 35.0 kg/m²; and a total body weight >50 kg (110 lb).

Informed Consent:

6. Capable of giving signed informed consent as described in [Appendix 1](#), which includes compliance with the requirements and restrictions listed in the ICD and in this protocol.

5.2. Exclusion Criteria

Participants are excluded from the study if any of the following criteria apply:

Medical Conditions:

1. Evidence or history of clinically significant hematological, renal, endocrine, pulmonary, gastrointestinal, cardiovascular, hepatic, psychiatric, neurological, or allergic disease (including drug allergies, but excluding untreated, asymptomatic, seasonal allergies at the time of dosing).
2. History of human immunodeficiency virus (HIV) infection, syphilis, hepatitis B, or hepatitis C; positive testing for HIV, syphilis, HBsAg, or HCVAb. Prior Hepatitis B vaccination is allowed.
3. Other medical or psychiatric condition including recent (within the past year) or active suicidal ideation/behavior or laboratory abnormality that may increase the risk of study participation or, in the investigator's judgment, make the participant inappropriate for the study.

Prior/Concomitant Therapy:

4. Use of prescription or nonprescription drugs and dietary and herbal supplements within 7 days or 5 half-lives (whichever is longer) prior to the first dose of study intervention. (Refer to [Section 6.5](#) for additional details).

Prior/Concurrent Clinical Study Experience:

5. Previous administration with an investigational drug within 4 months or 5 half-lives preceding the first dose of study intervention used in this study (whichever is longer).

Diagnostic Assessments:

6. A positive urine drug test.
7. Screening supine BP ≥ 140 mm Hg (systolic) or ≥ 90 mm Hg (diastolic), following at least 5 minutes of supine rest. If BP is ≥ 140 mm Hg (systolic) or ≥ 90 mm Hg (diastolic), the BP should be repeated 2 more times and the average of the 3 BP values should be used to determine the participant's eligibility.
8. Baseline 12-lead ECG that demonstrates clinically relevant abnormalities that may affect participant safety or interpretation of study results (eg, baseline QTc interval >450 msec, complete LBBB, signs of an acute or indeterminate-age myocardial infarction, ST-T interval changes suggestive of myocardial ischemia, second- or third-degree AV block, or serious bradyarrhythmias or tachyarrhythmias). If the baseline uncorrected QT interval is >450 msec, this interval should be rate-corrected using the Fridericia method and the resulting QTcF should be used for decision

making and reporting. If QTc exceeds 450 msec, or QRS exceeds 120 msec, the ECG should be repeated 2 more times and the average of the 3 QTc or QRS values should be used to determine the participant's eligibility. Computer-interpreted ECGs should be overread by a physician experienced in reading ECGs before excluding participants.

9. Participants with **ANY** of the following abnormalities in clinical laboratory tests at screening, as assessed by the study-specific laboratory and confirmed by a single repeat test, if deemed necessary:
 - AST **or** ALT level $\geq 1.25 \times$ ULN;
 - Total bilirubin level $\geq 1.5 \times$ ULN; participants with a history of Gilbert's syndrome may have direct bilirubin measured and would be eligible for this study provided the direct bilirubin level is \leq ULN.

Other Exclusions:

10. History of alcohol abuse or binge drinking and/or any other illicit drug use or dependence within 6 months of Screening. Binge drinking is defined as a pattern of 5 (male) and 4 (female) or more alcoholic drinks in about 2 hours. As a general rule, alcohol intake should not exceed 14 units per week (1 unit = 8 ounces (240 mL) beer, 1 ounce (30 mL) of 40% spirit or 3 ounces (90 mL) of wine).
11. Blood donation (excluding plasma donations) of approximately 400 mL or more within 60 days prior to dosing.
12. History of sensitivity to heparin or heparin-induced thrombocytopenia.
13. History of substance abuse within 12 months of the screening visit.
14. Pregnant females; breastfeeding females.
15. Unwilling or unable to comply with the criteria in the Lifestyle Considerations section of this protocol.
16. Investigator site staff or Pfizer employees directly involved in the conduct of the study, site staff otherwise supervised by the investigator, and their respective family members.

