1.3. Schedule of Activities

The SoA table provides an overview of the protocol visits and procedures. Refer to the **STUDY ASSESSMENTS AND PROCEDURES** section of the protocol for detailed information on each procedure and assessment required for compliance with the protocol.

The investigator may schedule visits (unplanned visits) in addition to those listed in the SoA table, in order to conduct evaluations or assessments required to protect the well-being of the participant.

Visit Identifier Abbreviations used in this table may be found in Appendix 7 .	Screening	Single Dose and Post-Treatment Evaluation/Early Termination									
		Day -28 to Day -2	Day -1	Day 1	Day 2	Day 3	Day 8	Day 15	Day 30	Day 60	Day 90/ET
Visit Window (days)	-	0	0	0	0	±1	±2	±2	±2	±2	±5
Hours After Dose	-	-	0	24	48						
Informed consent	X										
CRU confinement		X	→	→	X						
Inclusion/exclusion criteria	X	X									
Medical/medication history (update)	X	X									
Physical exam (including height and body weight at Screening only) ^b	X	X									
Safety laboratory (≥10-hour fasting) (hematology, chemistry, urinalysis, coagulation)	X	X		X ^c	X	X	X	X	X	X	
Lipid panel ^d	X		X ^f	X ^c	X	X	X	X	X	X	
Extended lipoprotein panel ^e			X ^f				X		X	X	
Demography	X										
Pregnancy test (WOCBP only)	X	X						X	X	X	
Contraception check	X	X				X	X	X	X	X	
FSH ^g	X										
Urine drug testing	X	X									
12-Lead ECG	X		X ^h	X ^c			X			X	
Blood pressure and pulse rate	X		X ^h	X ^c	X	X	X			X	
HIV, HBsAg, HCVAb, syphilis test	X										
Study intervention administration			X ⁱ								
Pharmacokinetic blood sampling ^j			X	X	X	X	X	X	X	X	
Pharmacodynamic blood sampling (ANGPTL3)			X ^f	X ^c	X	X	X	X	X	X	

PFIZER CONFIDENTIAL

Visit Identifier Abbreviations used in this table may be found in Appendix 7 .	Screening	Single Dose and Post-Treatment Evaluation/Early Termination									
		Day -28 to Day -2	Day -1	Day 1	Day 2	Day 3	Day 8	Day 15	Day 30	Day 60	Day 90/ET
Days Relative to Day 1	Day -28 to Day -2	0	0	0	0	±1	±2	±2	±2	±2	±5
Visit Window (days)	-	0	24	48							
Hours After Dose	-	-	0								
CRU discharge					X						
Serious and nonserious adverse event monitoring	X	→	→	→	→	X	X	X	X	X	

- a. Day relative to start of study intervention (Day 1).
- b. A full physical examination may be done at screening or Day -1; otherwise brief physical exam envisioned for findings during previous PE or new/open AEs, at Investigator discretion.
- c. 24 hours post-dose.

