5.3.4. Contraception

The investigator or his or her designee, in consultation with the participant, will confirm that the participant has selected an appropriate method of contraception for the individual participant and his or her partner(s) from the permitted list of contraception methods (see [Appendix 4 Section 10.4.4](#)) and will confirm that the participant has been instructed in its consistent and correct use. At time points indicated in the schedule of activities ([SoA](#)), the investigator or designee will inform the participant of the need to use highly effective contraception consistently and correctly and document the conversation and the participant's affirmation in the participant's chart (participants need to affirm their consistent and correct use of at least 1 of the selected methods of contraception). In addition, the investigator or designee will instruct the participant to call immediately if the selected contraception method is discontinued or if pregnancy is known or suspected in the participant or partner.

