6.5. Concomitant Therapy

Use of prescription or nonprescription drugs and dietary and herbal supplements are prohibited within 7 days or 5 half-lives (whichever is longer) prior to the first dose of study intervention. Limited use of nonprescription medications that are not believed to affect participant safety or the overall results of the study may be permitted on a case-by-case basis following approval by the sponsor. Acetaminophen/paracetamol may be used at doses of ≤ 1 g/day.

All concomitant treatments taken during the study must be recorded with indication, daily dose, and start and stop dates of administration. All participants will be questioned about concomitant treatment at each clinic visit.

Treatments taken within 28 days before the first dose of study intervention will be documented as a prior treatment. Treatments taken after the first dose of study intervention will be documented as concomitant treatments.

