8.2.5. Pregnancy Testing

Pregnancy tests may be urine or serum tests, but must have a sensitivity of at least 25 mIU/mL. Pregnancy tests will be performed in WOCBP at the times listed in the [SoA](#). Following a negative pregnancy test result at screening, appropriate contraception must be commenced and a second negative pregnancy test result will be required at the baseline visit prior the participant's receiving the study intervention. Pregnancy tests will also be done whenever 1 menstrual cycle is missed during the active treatment period (or when potential pregnancy is otherwise suspected) and at the end of the study. Pregnancy tests may also be repeated if requested by IRBs/ECs or if required by local regulations.

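### Does the pre-dose drug washout conflict with the hormonal contraceptives and HRT in Appendix 4 badly enough to change the plan?

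*Protocol*

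**What the plan says.** **The washout.** Protocol Section 5.2 opens with "Participants are excluded from the study if any of the following criteria apply", and criterion 4 lists "Use of prescription or nonprescription drugs and dietary and herbal supplements within 7 days or 5 half-lives (whichever is longer") before the first dose, pointing to Section 6.5 for detail. Section 6.5 says the same: "Use of prescription or nonprescription drugs and dietary and herbal supplements are prohibited within 7 days or 5 half-lives (whichever is longer"). It then gives two reliefs. One is that "Limited use of nonprescription medications that are not believed to affect participant safety or the overall results of the study may be permitted" case by case with sponsor approval; the other is low-dose paracetamol. Hormonal contraception and HRT are not mentioned in either place. Sections 5 and 8 rule out waivers.

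**The contraception rules.** Inclusion 1 (Section 5.1) refers to Appendix 4. Section 10.4.2 asks a woman of childbearing potential to use an acceptable method for at least 21 weeks after the last dose. Section 10.4.4 lists 12 methods, several of them hormonal. Section 10.4.3 lets a woman on HRT whose menopausal status is in doubt continue it, provided she uses a nonestrogen hormonal method of the highly effective kind.

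**Timing.** Section 8.2.5 states: "Following a negative pregnancy test result at screening, appropriate contraception must be commenced". The Schedule of Activities (Section 1.3) has a row, "Contraception check", marked at Screening and Day -1. Section 5.3.4 adds that "participants need to affirm their consistent and correct use of at least 1 of the selected methods of contraception", chosen "from the permitted list of contraception methods".

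**The concern.** One part of the protocol appears to forbid what another part offers. Contraception has to be under way before dosing and is checked on Day -1. A hormonal method in use that day lies inside even the shortest washout of 7 days. Any single exclusion criterion excludes, and waivers are not allowed. On the literal text, a woman who chose a hormonal method from the permitted list and used it up to dosing would be ineligible, and enrolling her would be an eligibility deviation.

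A second strand concerns the standard of contraception. Section 5.3.4 has the investigator tell participants to use *highly effective* contraception, while Sections 4.2 and 10.4.2 ask for an *acceptable* method. The Section 10.4.4 list is not divided into tiers and includes a condom alone. Section 5.3.4 belongs to the Lifestyle Considerations, and Exclusion 15 makes compliance with these an entry condition.

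At stake are who may enter and how consistently the criterion is applied.

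**Working it through.** The trial has no hypothesis and no power calculation (Sections 9.1 and 9.2), so there is no planned figure to reproduce. The check is a comparison of passages and one count.

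**1. Which listed methods meet the literal washout?** Section 10.4.4 has 12 items.

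| Group | Items | Count |
|---|---|---|
| Combined and progestogen-only products | 6, 7, 9 | 3 |
| Implant and hormone-releasing intrauterine system | 1, 3 | 2 |
| Non-hormonal | 2, 4, 5, 8, 10, 11, 12 | 7 |

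- If a device placed earlier counts as drug use: 3 + 2 = 5 of 12 caught, and 12 − 5 = 7 free.
- If it does not: 3 of 12 caught, and 12 − 3 = 9 free.
- Three is not a firm lower limit. Section 6.5 lets the sponsor approve a nonprescription product, and the documents do not give the prescription status of items 6, 7 and 9.
- Spermicide is not counted as a drug here. If it were, items 11 and 12 would also need that approval, leaving 7 − 2 = 5 clearly free in the first case (item 10 can be used without it).

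These are list items, not participants. The documents give no sex split or contraceptive mix, so the number of women affected cannot be computed.

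**2. Can both rules be met together?** Yes, for contraception. A woman using a non-hormonal item before dosing satisfies Section 8.2.5, the Day -1 check and Exclusion 4. The washout applies only before the first dose, so its text does not bar starting a listed hormonal method afterwards. For these women the washout narrows the list without emptying it.

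**3. The HRT sentence.** Here the tension is direct. Continuing HRT through the study means taking it before dosing, and the washout has no exception for it. The clause covers only women on HRT whose menopausal status is in doubt. It also offers the alternative of stopping HRT so that status can be confirmed before enrolment.

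**4. The two standards.** Sections 4.2, 5.3.4 and 10.4.2 all lead to Appendix 4, and Section 5.3.4 itself treats Section 10.4.4 as the permitted list. The working test is therefore the same throughout: choose from the list and affirm use. The undefined term sets a condition in only two places: the HRT clause, and item 5 of Section 10.4.4 when the conditions for a vasectomized partner are not met.

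**5. What changes under each reading?**

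| | Literal: washout governs | Appendix 4 read as the specific rule |
|---|---|---|
| Woman on a hormonal method up to dosing | Not eligible | Eligible |
| Woman on a non-hormonal method | Eligible | Eligible |
| Planned size | 9 per cohort, 18 in all | Same |
| Analysis sets (Protocol 9.3, SAP 4) | Same definitions | Same definitions |
| Endpoints and summaries | Same | Same |

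The analysis sets depend on enrolment, treatment and available data, not on freedom from eligibility deviations. A woman whose entry was later judged a deviation would stay in the sets for which she has data. The criterion is the same for both cohorts, so neither reading favours one dose over the other.

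**The case for a change.** The strongest case for acting is that eligibility is applied as written. The drafters thought about exceptions in Section 6.5 and wrote two, so silence on hormonal products is hard to read as a third. Nothing says that Appendix 4 overrides Section 5.2, and the ban on waivers means the point cannot be settled woman by woman. Two careful readers could decide differently on the same participant. The repair would cost only amendment wording.

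Much of this stands. The exemption is missing, and the HRT sentence and the two uses of *highly effective* as a condition are loose. What does not stand is that the hormonal options are simply unusable at entry. The sponsor-approved nonprescription route is part of the protocol, so using it is not a waiver. Inclusion 1 also expressly brings in Appendix 4, whose method list and HRT clause are more specific than a general washout. That points to an omission in drafting rather than two opposed intentions. The link through Exclusion 15 adds little, since Section 5.3 presents its content as guidelines and Section 5.3.4 accepts any method from the list. Low cost is no reason for a change that brings no gain in safety, bias or precision, and none has been shown.

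**Conclusion.** The wording conflict is real, but it does not call for a change to the plan. Up to 5 of 12 listed methods are caught by a literal reading, 3 if the implant and the intrauterine system are not counted as drug use, and possibly fewer if a nonprescription product is approved. Seven to nine satisfy both rules, enrolment is not blocked, and a trial run exactly as written would still give sound results. The counts assume that spermicide is not a drug.

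What remains is a clarification for the sponsor: Exclusion 4 and Section 6.5 should be reconciled with Section 8.2.5 and Appendix 4, and the methods meant by *highly effective* identified where the term sets a condition. Which rule is right is a clinical matter on which this review takes no position.

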5.3. Lifestyle Considerations

The following guidelines are provided:

5.3.1. Meals and Dietary Restrictions

- Participants must abstain from all food and drink (except water) for ≥ 10 hours prior to any safety laboratory evaluations.

- While participants are confined, their total daily nutritional composition should be approximately 55% carbohydrate, 30% fat, and 15% protein. The daily caloric intake per participant should not exceed approximately 3200 kcal.

5.3.2. Caffeine, Alcohol, and Tobacco

- Participants will abstain from caffeine-containing products for 24 hours prior to the start of dosing and during confinement in the CRU.
- Participants will abstain from alcohol for 24 hours prior to admission to the CRU and continue abstaining from alcohol during confinement in the CRU. Participants may undergo an alcohol breath test or blood alcohol test at the discretion of the investigator.
- Participants will abstain from the use of tobacco- or nicotine-containing products for 24 hours prior to dosing and during confinement in the CRU.

5.3.3. Activity

- Participants will abstain from strenuous exercise (eg, heavy lifting, weight training, calisthenics, aerobics) for at least 48 hours prior to each blood collection for clinical laboratory tests. Walking at a normal pace will be permitted;

5.3.4. Contraception

The investigator or his or her designee, in consultation with the participant, will confirm that the participant has selected an appropriate method of contraception for the individual participant and his or her partner(s) from the permitted list of contraception methods (see [Appendix 4 Section 10.4.4](#)) and will confirm that the participant has been instructed in its consistent and correct use. At time points indicated in the schedule of activities ([SoA](#)), the investigator or designee will inform the participant of the need to use highly effective contraception consistently and correctly and document the conversation and the participant's affirmation in the participant's chart (participants need to affirm their consistent and correct use of at least 1 of the selected methods of contraception). In addition, the investigator or designee will instruct the participant to call immediately if the selected contraception method is discontinued or if pregnancy is known or suspected in the participant or partner.

5.4. Screen Failures

Screen failures are defined as participants who consent to participate in the clinical study but are not subsequently randomly assigned to study intervention. Screen failure data are collected and remain as source and are not reported to the clinical database.

Individuals who do not meet the criteria for participation in this study (screen failure) may not be rescreened.

